10.1.1 Inclusion criteria

Unless otherwise noted, inclusion criteria must be met at Screening, Biopsy, and prior to injection.

- 1. Male and female subjects, age 30 to 70 years on the date of informed consent.
- 2. Patients with type 2 diabetes mellitus (T2DM).
- 3. Patients with a well-established diagnosis of diabetic nephropathy as the underlying cause of their renal disease.
- At screening, patients not previously injected with NKA with CKD defined as a GFR of 20 50 mL/min/1.73m² inclusive. Patients previously treated with a single NKA injection with eGFR 15 to 60 mL/min may also enroll in this clinical trial.
- 5. Microalbuminuria that cannot be explained by an alternative diagnosis. Microalbuminuria is defined as urinary albumin-creatinine ratio (UACR) \ge 30 mg/g or urine albumin excretion \ge 30 mg/day on 24 hour urine collection.
- 6. Prior to biopsy, systolic blood pressure between 105 and 140 mmHg (inclusive) and diastolic blood pressure ≤90 mmHg.
- 7. Ongoing and stable treatment with ACEI or ARB initiated at least 8 weeks prior to enrollment. Treatment must be stable for the 6 weeks immediately prior to injection. Stable treatment is defined as dose adjustment to no less than ½ of the current dosage and no more than 2X the current dosage over the 6 week period immediately prior to injection; dose interruptions of up to 7 days due to medical necessity are allowed. Patients who are intolerant to ACEI or ARBs may be included as long as they have stable BP within the acceptable limits.
- 8. Minimum of 2 measurements of eGFR or sCr taken at least 3 months apart (prior to screening) and within the previous 12 months to define the rate of progression of CKD. The patient should have sufficient historical data to provide a reasonable estimate of the rate of progression of CKD as determined following consultation with the Medical Monitor (to insure sufficient data is available). In addition, the rate of progression of CKD must be consistent over time. There is no defined rate of progression that is required to qualify for inclusion.
- 9. Willing and able to refrain from use of NSAIDs (including aspirin) and clopidogrel, prasugrel, or other platelet inhibitors peri-procedure (i.e., before and after both the biopsy and injection). The wash-out period before and after each procedure should be 7 days. Willing and able to refrain from use of fish oil and dipryridamole for 7 days before and 7 days after each procedure.
- 10. Willing and able to cooperate with all aspects of the study.

```
Confidential
```

11. Willing and able to give signed informed consent.

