Randomization: Open-label, non-randomized.

Control Group: Each subject will serve as his or her own control; the patient's previous medical history, which must include a minimum 6 month period of observation of renal function, will serve as the comparator for rate of progression of renal insufficiency.

Sample Size: Up to 30 subjects will be injected with NKA. As this is a Phase II safety and efficacy study, robust statistical analysis will not be performed. Therefore, the sample size proposed for this study is a size typical for the active treatment group in Phase II studies, allowing for identification of safety outcomes and early efficacy in a limited population.

Study Population:

Male or female patients 30 to 70 years of age with Type 2 diabetes mellitus and CKD with eGFR between 20 and 50 mL/min/1.73m². An enrolled patient should have sufficient historical clinical data to determine his or her individual rate of CKD disease progression.

Inclusion Criteria: Unless otherwise noted, inclusion criteria must be met at Screening and prior to injection.

- 1. Male and female subjects, age 30 to 70 years on the date of informed consent.
- 2. Patients with type 2 diabetes mellitus (T2DM).
- 3. Patients with a well-established diagnosis of diabetic nephropathy as the underlying cause of their renal disease.
- At screening, patients not previously injected with NKA with CKD defined as a GFR of 20 50 mL/min/1.73m² inclusive. Patients previously treated with a single NKA injection with eGFR 15 to 60 mL/min may also enroll in this clinical trial.
- Microalbuminuria that cannot be explained by an alternative diagnosis. Microalbuminuria is defined as urinary albumin-creatinine ratio (UACR) ≥ 30 mg/g or urine albumin excretion ≥ 30 mg/day on 24 hour urine collection.
- 6. Prior to biopsy, systolic blood pressure between 105 and 140 mmHg (inclusive) and diastolic blood pressure ≤90 mmHg.
- 7. Ongoing and stable treatment with ACEI or ARB initiated at least 8 weeks prior to enrollment. Treatment must be stable for the 6 weeks immediately prior to injection. Stable treatment is defined as dose adjustment to no less than ½ of the current dosage and no more than 2X the current dosage over the 6 week period immediately prior to injection; dose interruptions of up to 7 days due to medical necessity are allowed. Patients who are intolerant to ACEI or ARBs may be included as long as they have stable BP within the acceptable limits.

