- 8. Minimum of 2 measurements of eGFR or sCr taken at least 3 months apart (prior to screening) and within the previous 12 months to define the rate of progression of CKD. The patient should have sufficient historical data to provide a reasonable estimate of the rate of progression of CKD as determined following consultation with the Medical Monitor (to insure sufficient data is available). In addition, the rate of progression of CKD must be consistent over time. There is no defined rate of progression that is required to qualify for inclusion.
- 9. Willing and able to refrain from use of NSAIDs (including aspirin) and clopidogrel, prasugrel, or other platelet inhibitors peri-procedure (i.e., before and after both the biopsy and injection). The wash-out period before and after each procedure should be 7 days. Willing and able to refrain from use of fish oil and dipryridamole for 7 days before and 7 days after each procedure.
- 10. Willing and able to cooperate with all aspects of the study.
- 11. Willing and able to give signed informed consent.

Exclusion Criteria: Patients may not be enrolled if they meet any of the exclusion criteria listed below. Criteria should be assessed at Screening and before injection unless noted otherwise.

- 1. Type 1 diabetes mellitus (DM).
- 2. History of a renal transplant.
- 3. HbA1c > 10% at Screening. Patients with HbA1c > 8% at the time of screening should be offered diabetic teaching and advised to consult their primary physicians for further diabetic management.
- 4. Hemoglobin levels < 9 g/dL prior to injection. Hemoglobin levels should be measured within 48 hours before the procedure or per site standard practice.
- 5. Known allergy to kanamycin or structurally similar aminoglycoside antibiotics (as kanamycin is used during manufacture of NKA).
- 6. Abnormal coagulation status as measured by APTT, INR, and/or platelet count at Screening.
- 7. Not a good candidate for the injection procedure (based on the assessment of the surgeon who will be performing the injection) including patients who are morbidly obese, have excessive fat surrounding the kidney, have BMI > 45, or who are otherwise at excessive risk for serious complications.
- 8. Clinically significant infection requiring parenteral antibiotics within 6 weeks of injection.
- 9. Patients with small kidneys (average size < 9 cm) or only one kidney, as assessed by MRI or renal US at screening or if previously done within 1 year of screening.

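### The own-control history must cover at least 6 months, but criterion 8 sets its floor at two values 3 months apart, which is too few to show the consistent rate it also requires

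*Combined protocol and SAP*

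**What the plan says.** The Control Group paragraph of the Protocol Synopsis states that "Each subject will serve as his or her own control". It adds that the previous medical history, which "must include a minimum 6 month period of observation of renal function, will serve as the comparator" for rate of progression. There is no concurrent control arm.

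Inclusion criterion 8, worded alike in the Synopsis and in Section 10.1.1, asks for a "Minimum of 2 measurements of eGFR or sCr taken at least 3 months apart (prior to screening) and within the previous 12 months". It then adds two conditions without numbers:

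- The history must be sufficient for a reasonable estimate of the rate, settled in consultation with the Medical Monitor.
- "In addition, the rate of progression of CKD must be consistent over time".

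The criterion gives no number of values for the second condition, no tolerance and no method for calculating a slope. It states that no particular rate is needed to qualify.

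The pre-injection rate is used in Section 14.7.3, where a paired t-test of the change in rate is optional. Section 14.6 (Efficacy Analysis) reads as not applicable.

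**The concern.** The Synopsis holds two different minimum histories for the same comparator: 6 months in one paragraph and 3 months in the criterion. Section 10.1.1, the full eligibility section, carries only the shorter one. A patient with two values 3 months apart and nothing earlier passes the numeric floor of criterion 8 and fails the Control Group paragraph.

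The criterion also asks for something its own floor cannot supply. Two values define one line exactly, so nothing is left over with which to judge whether the rate was steady.

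With no control arm, a before/after statement about rate of progression is only as good as the pre-injection slope. If that slope is poorly measured, an apparent stabilization after injection may only reflect error in the earlier estimate.

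**Working it through.** The plan states no slope, SD, power or sample size calculation, so there is no figure of its own to reproduce.

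**Inputs from the documents**
- Floor of criterion 8: 2 values, 3 months (0.25 yr) apart.
- Control Group paragraph: 6 months (0.5 yr).
- Up to 30 patients (Section 14.1).
- Efficacy follow-up to 6 months after the second injection (Section 14.2).
- Renal chemistry at screening, 3 to 1 days before biopsy, Day -14 to -10 and Day 0 (Section 4).
- Biopsy within 45 days of the first screening assessment (Section 11.1), and injection 4 to 14 weeks after biopsy (Section 11.2).

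**Assumptions, not in the documents**
- Within-patient SD of one eGFR value, s = 2 to 4 mL/min/1.73m².
- For illustration only, a true loss of 4 mL/min/1.73m² per year.

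**Step 1. Precision of one patient's slope.** SE = s / √Σ(t − t̄)², with t in years. For two values a gap g apart this is s√2/g, with 2 − 2 = 0 residual degrees of freedom.

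| Pre-injection values | SE, s = 2 | SE, s = 4 | Residual df |
|---|---|---|---|
| 2 values, 3 months apart | 2 × 1.414/0.25 = 11.3 | 22.6 | 0 |
| 2 values, 6 months apart | 2 × 1.414/0.5 = 5.7 | 11.3 | 0 |
| 3 values at 0, 3, 6 months | 5.7 | 11.3 | 1 |
| 5 values at 0, 3, 6, 9, 12 months | 2.5 | 5.1 | 3 |

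All SEs are in mL/min/1.73m² per year. The third row equals the second because a value at the mid-point adds nothing to Σ(t − t̄)². It buys a degree of freedom, not precision.

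**Step 2. Comparison with the on-study slope.** The visits are baseline, Days 7, 14 and 28 and months 2, 3 and 6, then the same days and months after a second injection at about 6.4 months. That is 13 visits over about 12.4 months. The same formula gives an SE of 1.7 to 3.4.

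**Step 3. What the floor does to one patient's history.** For a true loss of 4 per year, the chance that the estimated slope shows no decline is 1 − Φ(4/SE).
- 3 months: 1 − Φ(4/11.3) = 0.36 to 1 − Φ(4/22.6) = 0.43.
- 6 months: 1 − Φ(4/5.7) = 0.24 to 1 − Φ(4/11.3) = 0.36.

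**Step 4. Group mean, extreme case.** Suppose all 30 patients sit at the floor and true slope changes do not vary. The 95% half-width for the mean change is 1.96 × √(SE_pre² + SE_post²)/√30.
- 3 months: 1.96 × √(11.3² + 1.7²)/5.48 = 4.1, rising to 8.2 at s = 4.
- 6 months: 2.1 to 4.2.

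**Step 5. Adding the scheduled pre-injection samples.** Take historical values at months 0 and 3, screening at month 4, and add the four scheduled samples.
- Short schedule (biopsy 1 week after screening, injection 4 weeks later): SE about 5.7 to 11.5.
- Longest schedule (45 days, then 14 weeks): SE about 3.2 to 6.5.

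The overall range is about 3.2 to 11.5.

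**The case against.** **Two values are only a floor inside a rule with several parts.** This stands. A reader might infer that a patient with two values 3 months apart is eligible outright. The text does not go that far: that patient meets the numeric floor but must still satisfy the sufficiency and consistency conditions. What remains is that neither condition has a number, so nothing brings the floor up to 6 months.

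**Scheduled samples before injection would lengthen the series.** This stands in part. The Synopsis speaks of the rate before injection, and Step 5 shows that those samples would bring precision to about that of a 6-month span or better. But criterion 8 counts values before screening, and no rule puts the later samples into the slope. They are central-laboratory results, and Section 12.3 recognises that comparison with historical values may need a second analysis at the site laboratory.

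**The group figure in Step 4 is extreme.** This stands. It places every patient at the floor and ignores variation in true change. With an assumed SD of true change of 3 to 8 mL/min/1.73m² per year, the ratio of 3-month to 6-month half-widths falls from 1.94 to between 1.4 and 1.9.

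**The study is descriptive and the rate test is optional.** This also stands. A reader might infer that the primary objective can be judged only against the prior rate. The primary efficacy measure is serial creatinine and eGFR, change from baseline is summarised as well, and change in rate of progression is listed as exploratory. The history is the stated comparator for rate of progression, not for every outcome.

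**Conclusion.** The point holds on the text alone in two respects. The Control Group paragraph and criterion 8 set different minimum histories for the same comparator, and two values cannot show a consistent rate.

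The size rests on an assumed within-patient SD of 2 to 4. For a patient at the floor the slope SE is 11.3 to 22.6 mL/min/1.73m² per year, twice the 5.7 to 11.3 of a 6-month span and more than six times the on-study 1.7 to 3.4. It is a worst case, because the documents do not say how many patients will sit near the floor.

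A reader might also infer that this error exceeds any plausible true rate of decline. The documents give no rate of progression, so they cannot support that. It does exceed the 4 per year assumed here.

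Nor does a 6-month span make individual slopes precise. Even then, a patient truly losing 4 per year would show no decline in 24% to 36% of cases.

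**What to change.** Reconcile the Control Group paragraph with criterion 8 in the Synopsis and in Section 10.1.1:

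- Change criterion 8 to at least three eGFR or creatinine values spanning at least 6 months before screening. The protocol already requires that span, and three is the fewest values that leave anything with which to check consistency.
- Collect every value available in the 12-month look-back and use them all in the pre-injection slope. A third value at the mid-point does not by itself reduce the SE; a longer span and more values do (2.5 to 5.1 with five values over 12 months).
- Report any patient admitted with a shorter history outside the before/after comparison of rates.

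This is a wording amendment with no added study procedure. The downside is that some candidates with sparse records must wait for another routine creatinine or are not eligible. The documents do not allow their number to be estimated.

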10.1.2 Exclusion criteria

Patients may not be enrolled if they meet any of the exclusion criteria listed below. Criteria should be assessed at Screening, before the biopsy, and before injection unless noted otherwise.

- 1. Type 1 diabetes mellitus (DM).
- 2. History of a renal transplant.
- 3. HbA1c > 10% at Screening. Patients with HbA1c > 8% at the time of screening should be offered diabetic teaching and advised to consult their primary physicians for further diabetic management.
- 4. Hemoglobin levels < 9 g/dL prior to injection. Hemoglobin levels should be measured within 48 hours before the procedure or per site standard practice.
- 5. Known allergy to kanamycin or structurally similar aminoglycoside antibiotics (as kanamycin is used during manufacture of NKA).
- 6. Abnormal coagulation status as measured by APTT, INR, and/or platelet count at Screening.
- 7. Not a good candidate for the injection procedure (based on the assessment of the surgeon who will be performing the injection) including patients who are morbidly obese, have excessive fat surrounding the kidney, have BMI > 45, or who are otherwise at excessive risk for serious complications.
- 8. Clinically significant infection requiring parenteral antibiotics within 6 weeks of injection.
- 9. Patients with small kidneys (average size < 9 cm) or only one kidney, as assessed by MRI or renal US at screening or if previously done within 1 year of screening.
- 10. Patients with a rapid decline in renal function over the last 3 months prior to injection or acute kidney injury.
- 11. Patients with any of the following conditions prior to injection: renal tumors, polycystic kidney disease, renal cysts or other anatomic abnormalities that would interfere with injection procedure (e.g., cysts in the pathway of the injection for injection), hydronephrosis, skin infection over proposed injection sites, or evidence of a urinary tract infection.
- 12. Female subjects who are pregnant, lactating (breast feeding) or planning a pregnancy during the course of the study, or who are of child bearing potential and not using a highly effective method of birth control (including sexual abstinence). A highly effective method of birth control is defined as one that results in a low failure rate (i.e. less than 1 percent per year) when used consistently and correctly, such as injections, injectables, combined oral contraceptives, some intrauterine devices (IUDs), sexual abstinence, or a vasectomized partner. Subjects must be willing to continue birth control methods throughout the course of the study.
- 13. History of cancer within the past 3 years (excluding non-melanoma skin cancer and carcinoma in situ of the cervix).
- 14. Life expectancy of less than 2 years.
- 15. Any contraindication or known anaphylactic or severe systemic reaction to either human blood products or materials of animal (bovine, porcine) origin or anesthetic agents.
- 16. Positive for Human Immunodeficiency Virus (HIV), Hepatitis B Virus (HBV), or Hepatitis C Virus (HCV) assessed at the Screening Visit.
- 17. Subjects with active tuberculosis (TB) requiring treatment in the past 3 years.

- 18. Immunocompromised subjects or patients receiving immunosuppressive agents (including patients treated for chronic glomerulonephritis) within 3 months of injection. [Note: inhaled corticosteroids and chronic low-dose corticosteroids [≤ 7.5mg per day] are permitted as are brief pulsed corticosteroids for intermittent symptoms (e.g. asthma).]
- 19. Subjects with uncontrolled diabetes (defined as metabolically unstable by the PI), or with incapacitating cardiac and/or pulmonary disorders.
- 20. History of active alcohol and/or drug abuse that in the investigator's assessment would impair the subject's ability to comply with the protocol.
- 21. Patients with clinically significant hepatic disease (ALT or AST > 3.0 x ULN) at Screening.
- 22. Patients with bleeding disorders that would, in the opinion of the Investigator, interfere with the performance of study procedures; patients taking coumarins (e.g. Warfarin) or other anticoagulants (e.g. enoxaparin or direct thrombin inhibitors).
- 23. Any circumstance in which the investigator deems participation in the study is not in the subject's best interest.
- 24. Use of any investigational product within 3 months of the injection without receiving prior written consent of the Medical Monitor.

10.2 Prohibited and Concomitant Medications

Use of investigational drugs is prohibited during the course of the study unless preapproved for use by the Medical Monitor. Investigational drugs are defined as drugs which have not been approved for any use by the FDA.

Patients should avoid taking drugs with nephrotoxic potential during the course of the study, including for example chronic use of ibuprofen and other NSAIDs. Aspirin, up to a dose of 100 mg/day, may be taken for cardiovascular prophylaxis. NSAIDs may be taken PRN but the site should emphasize with patients the need to minimize use of NSAIDs during the course of the study.

Patients who are not intolerant of such agents must be on an ACEI or ARB for 8 weeks prior to enrollment (i.e., at the time of injection) and a stable regimen for 6 weeks prior to injection. Requiring a minimum of 8 weeks treatment prior to enrollment ensures that the patient will be on an ACEI or ARB for a minimum of 12 weeks before administration of the Investigational Product. Stable regimen is defined as a dose no less than ½ of the current dosage and no more than 2X the current dosage over the course of the 6 weeks immediately prior to injection. The ACEI or ARB dose should be the maximum tolerated dose for that patient. In addition, except where medically necessary, no changes should be made to ACEI or ARB dosing regimen from baseline through the 12 month EOS visit. A dose interruption of up to 7 days for medical necessity is allowed. Patients who are intolerant to ACEI or ARB therapy and, therefore, not taking an ACEI or ARB may be enrolled as long as their blood pressure is stable and within the acceptable range.

Medications which specifically interfere with measurements of sCr should be avoided including trimethoprim, dronedarone, and cimetidine. If such medications are required based on medical necessity, then the circumstance should be discussed with the medical monitor and the medication noted on the CRF.

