- 22. Patients with bleeding disorders that would, in the opinion of the Investigator, interfere with the performance of study procedures; patients taking coumarins (e.g. Warfarin) or other anticoagulants (e.g. enoxaparin or direct thrombin inhibitors).
- 23. Any circumstance in which the investigator deems participation in the study is not in the subject's best interest.
- 24. Use of any investigational product within 3 months of the injection without receiving prior written consent of the Medical Monitor.

Number of Sites: Up to 10 clinical centers will be included in the study.

Study Duration: 18 months NKA injections follow up followed by 24 month long term follow up for a total study duration of 42 months.

Study Enrollment: Up to 30 subjects undergoing NKA injection will be enrolled into the study. Patients who have received a single injection of NKA under previous research protocols may enroll in this clinical trial to receive a single additional injection. Patients who have never received an NKA injection may enroll in this clinical trial for up to a total of two (2) NKA injections, temporally spaced at least 6 months apart. All biopsies are to be taken from a single kidney, and all NKA injections are to be given into the kidney that was biopsied. Patients who complete screening procedures satisfying all I/E criteria will be enrolled into the study immediately prior to the injection. Patients who do not meet all criteria before injection will be considered screen failures. Once a patient has been injected, the patient will have completed treatment and every effort should be made to ensure the patient completes all follow-up visits. Injection dates for the first 3 patients receiving their second NKA injection will be staggered by a minimum of 3 week intervals to allow for assessment of acute adverse events and other safety parameters by the DSMB. Subsequent second injections will continue to be staggered so as to occur no less than 3 weeks apart, but individual DMSB review will not be required. At the completion of the follow-up visits, patients will continue in a long-term follow-up study. Patients will be followed for a total of 36 months following the last NKA injection under this protocol, whether the first or second injection.

Investigational Plan:

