6.1.3 Standard of Care

There is no cure for CKD or therapy which prevents progression of disease. Therefore, treatment of patients with chronic kidney disease is focused on managing comorbid conditions including cardiovascular disease while slowing progression and preparing for kidney failure and kidney replacement.

Co-morbidities: Anemia, mineral and bone disorders, and cardiovascular events are the major comorbidities requiring treatment in CKD patients. Anemia is often treated via recombinant human erythropoietin. In addition, anti-inflammation medications may also be administered to temper inflammatory cytokines. Treatment for mineral and bone disorders focus on maintaining phosphorous and calcium homeostasis (Lee et al., 2007). Initial treatment restricts dietary phosphorus intake or uses specific phosphate binders when phosphate or parathyroid hormone levels begin to rise. For chronic therapy, calcium-based phosphate binders are the most widely prescribed treatments for management of CKD-associated hyperphosphatemia. Additionally,

vitamin D and its related compounds may be administered to raise serum calcium concentration sufficiently to suppress parathyroid hormone secretion. Increased risk of cardiovascular disease can be a complication of CKD or an independent comorbidity, with the former being probable in advanced CKD cases (Gerstein et al., 2001). The use of 1) angiotensin converting enzyme inhibitors (ACEI) and/or angiotensin receptor blockers (ARBs) to reduce proteinuria and control hypertension, 2) insulin titration to achieve appropriate glycated hemoglobin, and 3) statin therapy to counter dyslipidemia, collectively aim to reduce cardiovascular risk and prevent or slow the progression of kidney failure.

Renal replacement therapy: When a patient reaches Stage 5 CKD, renal replacement therapy (i.e. dialysis or kidney transplant) is indicated. The vast majority of Stage 5 individuals receive hemodialysis (Dhingra et al., 2001). Dialysis replaces about 5-15% of kidney function depending on the intensity and frequency of use, and helps restore fluid and electrolyte balance when kidneys fail.

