10 STUDY POPULATION

10.1 Eligibility Criteria

Eligibility criteria should be assessed at Screening. In addition, unless otherwise noted for the specific criterion, eligibility criteria should be also be reviewed before the biopsy and at the Day -10 to -14 pre-injection visit.

Up to 30 subjects will be enrolled in this study, including subjects previously injected in either Phase 1 trial. Note that a subject will be considered enrolled into the study at the time of injection.

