11.2 Biopsy (4 to 14 Weeks before Injection)

The biopsy should be scheduled within 45 days following the first screening assessment. The biopsy should be scheduled so that the injection procedure can be scheduled at 4 weeks or later. Due to shipping and manufacturing schedules, the preferred days for collecting the biopsy are Wednesday or Thursday. Biopsies should not be collected on a Friday.

Patients should report to the site one to three days before the biopsy for pre-biopsy assessments. As much as possible, pre-biopsy laboratory samples may be collected and assessed to verify patient eligibility prior to biopsy.

Following final review of appropriate eligibility criteria, the biopsy should be performed as described below in Section 12.5.1. The biopsy should be sent to RegenMed (Cayman) Ltd. in the shipping container provided by RegenMed (Cayman) Ltd. according to procedures detailed in the Study Reference Manual. After the biopsy, the patient should remain in the hospital overnight for observation. As long as any biopsy-related AEs have resolved, stabilized, or returned to baseline, the patient may be discharged the same day as biopsy per site standard practice.

Once the biopsy is received at RegenMed (Cayman) Ltd., the biopsy will be assessed and processed according to RegenMed (Cayman) Ltd.'s SOPs for product manufacturing. One to two weeks after receiving the biopsy in North Carolina, RegenMed (Cayman) Ltd. will notify the site concerning the adequacy of the sample for manufacture of NKA. Following the notification to proceed, the site can confirm the injection date. If the biopsy cannot be used for manufacture of NKA, the patient should be discontinued from the study.

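### The stated 12-week ACEI/ARB run-in and the end date of the regimen freeze conflict with other sections; separately, nothing ties the historical comparator to ACEI/ARB exposure

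*Combined protocol and SAP*

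**What the plan says.** **Run-in.** Section 10.2 states that patients who are not intolerant "must be on an ACEI or ARB for 8 weeks prior to enrollment (i.e., at the time of injection"), and that this "ensures that the patient will be on an ACEI or ARB for a minimum of 12 weeks before administration of the Investigational Product". Section 10.1 defines the reference point: "Note that a subject will be considered enrolled into the study at the time of injection". The synopsis agrees that eligible patients "will be enrolled into the study immediately prior to the injection".

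**Freeze.** Section 10.2 asks for no ACEI/ARB change, except where medically necessary, "from baseline through the 12 month EOS visit". A footnote to the laboratory schedule puts end of study (EOS) at the Month 18 visit. Sections 9 and 11.4 put it 18 months after the second injection.

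**Comparator.** The synopsis makes each patient's own history the comparator for the rate of progression. Inclusion criterion 8 (Section 10.1.1) asks for at least two eGFR or creatinine values, at least 3 months apart, before screening and "within the previous 12 months to define the rate of progression of CKD". It sets no condition on ACEI/ARB use when those values were taken. Section 6.1.3 lists ACEI/ARB with insulin titration and statins as treatments that collectively aim to reduce cardiovascular risk and "prevent or slow the progression of kidney failure".

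**The concern.** There are three separate points. The first two are conflicts of wording: a stated design property that does not follow from its own rule, and a freeze that ends at a visit other sections place later.

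The third concerns the comparison itself. There is no concurrent control. If a patient started ACEI/ARB late in the historical period, or after it, the rate before injection is partly or wholly off treatment and the rate after injection is on treatment. A product with no effect could then appear to slow progression. The only inferential test the plan names, the optional paired t-test on change in rate of progression (Section 14.7.3), would carry that difference. Section 14.6 (Efficacy Analysis) is marked not applicable, so no adjustment is planned elsewhere.

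**Working it through.** **1. Run-in.** Minimum run-in = 8 weeks + (enrollment-to-injection interval).

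- Enrollment at injection, as the protocol defines it: 8 + 0 = 8 weeks. The stated 12 is not reproduced; the shortfall is 4 weeks, one third.
- Enrollment at biopsy: Section 11.2 is headed "Biopsy (4 to 14 Weeks before Injection"), so 8 + 4 = 12 weeks. This gives the stated figure but contradicts Sections 2, 10.1 and 10.2.
- Enrollment at screening: about 8 + 4 = 12 weeks for a biopsied patient. A returning patient with enough frozen cells skips biopsy and could have 8 weeks + 10 days = 9.4 weeks.

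**2. Freeze.** Months are counted from the first injection. Section 11.4 places the second injection 10 to 14 days after the Month 6 visit. Taking 30.4 days per month, these add 0.33 to 0.46 month.

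- The primary efficacy window (6 months after the second injection) ends at Month 12.33 to 12.46. A freeze to Month 12 misses its last 10 to 14 days.
- The secondary laboratory window (12 months after the last injection) ends at Month 18.33 to 18.46. Uncovered: 6.33/12 to 6.46/12 = 53% to 54%.
- EOS at 18 months after the second injection falls at Month 24.33 to 24.46, about 12.3 to 12.5 months after the freeze ends.
- A patient with one injection under this protocol has a 12-month secondary window, which is covered.

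**3. Historical rate.** On-treatment weeks before screening = max(0, run-in − gap), where gap is screening to injection. Off-treatment share = 1 − (on-treatment weeks)/(history length). The case is a new, ACEI/ARB-tolerant patient who started at the minimum, with the history running up to screening. The shortest gap is about 4 weeks. History lengths are 13 weeks (criterion 8), 26 weeks (the 6 months of observation in the synopsis control paragraph) and 52 weeks.

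| Run-in | Gap | On treatment before screening | Off share: 13 wk | 26 wk | 52 wk |
|---|---|---|---|---|---|
| 8 wk | 4 wk | 4 wk | 9/13 = 69% | 22/26 = 85% | 48/52 = 92% |
| 8 wk | 8 wk or more | 0 wk | 100% | 100% | 100% |
| 12 wk | 4 wk | 8 wk | 5/13 = 38% | 18/26 = 69% | 44/52 = 85% |

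The 12-week row shows that delivering the stated run-in would not cure the problem. The earliest required historical value lies at least 13 + 4 = 17 weeks before injection, outside both figures.

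**4. Size, illustration only.** Spurious benefit = f × d, where f is the share of patients who start after their history and d is the flattening of slope on treatment. Neither is in the documents. Assuming f = 25% to 100% and d = 1 to 4 mL/min/1.73 m² per year gives 0.25 to 4.0. For a middle case, f = 50% and d = 2, the shift is 1.0. With n = 30, a two-sided 5% paired t-test and an inert product, the chance of a significant result favouring NKA rises from a nominal 2.5% to 14%, 7.6% or 5.0% for an assumed SD of slope change of 6, 10 or 17.

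**The case against.** The best defence is that partial safeguards exist. Inclusion criteria apply at screening, biopsy and injection, so ACEI/ARB should already be ongoing at screening. Criterion 8 requires progression to be consistent over time and the Medical Monitor to be consulted. Section 12.2.4 records drugs affecting renal hemodynamics from consent onward. These help but do not close the gap. Treatment ongoing at screening says nothing about earlier values, consistency cannot be judged from two points, and recording begins after the historical values were taken.

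Several stronger readings are tempting, and the documents do not support them:

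- **That the run-in or freeze errors cause the off-treatment history.** They do not. The cause is the missing link between historical values and exposure; the freeze concerns follow-up only.
- **That every follow-up value is on treatment.** Intolerant patients may enrol and are off treatment in both periods, so this mechanism does not bias them. Interruptions of up to 7 days and medically necessary changes are also allowed.
- **That the screening-to-injection gap has a firm maximum of 45 days + 14 weeks = 143 days.** Sections 11.1 and 11.3 permit delays. Footnote 1 to three of the schedules instead puts screening within 45 days (6.4 weeks) of injection. On that reading 8 − 6.4 = 1.6 treated weeks precede screening, and the off share of a 13-week history is at most 11.4/13 = 88%.
- **That the freeze gap threatens the primary efficacy result.** On schedule it is about two weeks. It grows if the second injection is postponed, as the synopsis allows. A reader might also count the 12 months from the second injection, which would reach about Month 18 and close the gap, but Section 10.2 does not say so.

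It is also fair that Section 6.1.3 describes the joint aim of three treatments and gives no ACEI/ARB-specific effect on slope, and that the paired t-test is optional.

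**Conclusion.** The concern holds as three separate points. First, the rule as written guarantees 8 weeks of ACEI/ARB before product, not 12. Second, the freeze is tied to an EOS timing that conflicts with two other timings. For a new patient reinjected at about Month 6 it leaves about two weeks of the primary window and about half of the secondary laboratory window uncovered, and later dose changes could push the result either way. Third, and independently, the historical rate can be partly or wholly off treatment in tolerant patients who started recently. The likely direction favours NKA, resting on the protocol's own account of what these treatments are for.

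A reader might infer a definite amount of bias in the trial estimate. The documents do not support one: the share of recent starters, the drug effect on slope and the SD of slope change are all absent, so the f × d range shows sensitivity only. This should be fixed because the historical rate is the only comparator and the remedy is cheap.

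**What to change.** 1. Reconcile the 8-week rule, the 12-week statement and the definition of enrollment. Reconcile the freeze end point in Section 10.2 with the EOS timings in the schedules and Sections 9 and 11.4. These are decisions for the sponsor; no clinical rule is proposed here.
2. Record the ACEI/ARB start date and all dose changes from the earliest historical value used up to injection. The period must run to injection because a patient who starts at or after screening has a wholly off-treatment history.
3. Prespecify one sensitivity analysis: repeat the before/after comparison of rate (the paired t-test in Section 14.7.3) without patients who started or changed ACEI/ARB in that period. Report how many are removed, and keep intolerant patients who were untreated throughout.

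Estimating the historical rate from on-treatment values only, or adding a time-varying treatment term, is less dependable. Criterion 8 guarantees only two points, so recent starters may have no estimable rate, and a time-varying term would be weakly identified with at most 30 patients.

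The cost is wording changes, one added data item, and fewer patients and lower precision in the sensitivity analysis.
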